**The following documents are currently attached to this item:**

*There are no documents attached for this item.*

**Deception**

Does your project use deception? Deception could be considered any direct misinformation presented to the subject or omission of key information pertaining to the design or nature of the project.

No

**International Research**

Are you conducting research outside of the United States?

No

**Analysis Plan**

To analyze GUIDE's impact on the proximal and distal outcomes as detailed in our Theory of Change model (i.e., mental health/wellbeing, social connectedness and personal growth; work engagement and burnout) (attached), secondary outcomes from the trial (pre-post) will be analyzed either using linear mixed models or repeated-measures ANOVA, depending on whether there are clustering variables (e.g., workplace, first responder/veteran). Key measures used for this analysis will be the: PERMA-Profiler overall wellbeing score and subscales (Positive emotion, Engagement, Relationships, Meaning, Accomplishment), PHQ-8 (depression), GAD-7 (anxiety), WHO-5 (wellbeing), the Personal Wellbeing Score (PWS), DERS-SF (emotional regulation), UWES (work engagement), and MBI (burnout). We predict that participants with access to the GUIDE App during the trial will show improved positive emotion, engagement, relationships, meaning, accomplishment, wellbeing, work engagement and emotional regulation; as well as reduced burnout and symptoms of depression and anxiety, when compared to the waitlist group. We do not predict significant differences between the immediate and immediate with incentives groups. To assess how GUIDE app engagement relates to secondary outcomes, we will use exploratory analyses to examine the relationships between app engagement (total and by feature) to all secondary outcomes (delta between pre-post) using Pearson correlation coefficients. We will also report on the extent to which participants engage in the GUIDE App, total and per feature, for lessons completed, courses completed, small group posts, small group comments, wellness check-ins, journal entries, meditation sessions, badges earned and other usage metrics. The feasibility, acceptability, appropriateness and usability of the app will also be reported on with descriptive statistics to assess implementation and technical merit.

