## **Objectives**

### **Overall objectives**

The primary goal of this project is to test whether the GUIDE App promotes wellness and builds resilience in first responders, soldiers and veterans. Using a randomized three-arm pilot feasibility trial (immediate app access, immediate app access with incentives, waitlist), we will investigate whether the GUIDE App impacts mental health/wellness, social connectedness and personal growth; how app engagement relates to secondary outcomes, including work engagement and burnout; the extent to which participants engage in the app; as well as whether the GUIDE App is feasible, acceptable, appropriate, and usable. In our Theory of Change Model (attached), we propose that engagement with the Community, Wisdom, and Daily Practice features in GUIDE app will lead to improved proximal outcomes of mental health/wellbeing, social connectedness, and personal growth, and that these improvements will in turn will improve distal outcomes by increasing work engagement and reducing burnout.

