### **Primary outcome variable(s)**

The primary proximal outcome for this trial is mental health/wellbeing. This will be tested using: the overall score and Positive emotion subscale of the PERMA-Profiler, the Patient Health Questionnaire for depression symptoms (PHQ-8), the Generalized Anxiety Disorder-7 (GAD-7), the World Health Organization Five Well-Being Index (WHO-5), the Personal Wellbeing Score (PWS), and the Difficulties in Emotion Regulation Scale Short Form (DERS-SF). The primary outcome variable will be the overall wellbeing score of the PERMA-Profiler.

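### The analysis plan does not say how baseline enters the model for the primary outcome; adjusting for baseline PERMA overall would be at least as precise as the change-score analysis the wording permits

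*Combined protocol and SAP*

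**What the plan says.** Primary outcome variable(s) sets out a domain and then one variable within it: "The primary proximal outcome for this trial is mental health/wellbeing", and "The primary outcome variable will be the overall wellbeing score of the PERMA-Profiler".

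The Analysis Plan is the only section that names a model. It states that "secondary outcomes from the trial (pre-post) will be analyzed either using linear mixed models or repeated-measures ANOVA, depending on whether there are clustering variables", with workplace and first responder/veteran as its examples of clustering variables. PERMA overall comes under that sentence: "Key measures used for this analysis will be the: PERMA-Profiler overall wellbeing score and subscales". No separate primary analysis, baseline covariate, model term, contrast or alpha is given.

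The comparison appears as a prediction: "We predict that participants with access to the GUIDE App during the trial will show improved positive emotion", with further improvements listed, relative to the waitlist. For the two app arms: "We do not predict significant differences between the immediate and immediate with incentives groups". The section does not say which test carries the prediction. It could be the pooled app arms against waitlist, each app arm against waitlist, or the three-arm group-by-time test.

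The exploratory engagement analysis correlates usage with "all secondary outcomes (delta between pre-post) using Pearson correlation coefficients". That wording covers the correlations only.

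Procedures shows that the same scales are collected before and after the trial in all three arms.

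**The concern.** Overall objectives states: "The primary goal of this project is to test whether the GUIDE App promotes wellness and builds resilience in first responders, soldiers and veterans". The Abstract likewise says the trial is run to test effectiveness. The precision of the app-versus-waitlist difference on PERMA overall therefore matters, even in a pilot feasibility trial of up to 150.

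The plan ties the choice of model to clustering and says nothing about how baseline is handled. One of the two named options, repeated-measures ANOVA, compares change scores between arms. The other, a mixed model, may or may not do the same, depending on whether baseline means are free or common across arms. An analyst following the text could use the less precise form although every participant's baseline score has been requested. The reader also cannot tell which of several defensible tests answers the stated prediction.

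**Working it through.** **Inputs from the documents.** Three arms of 50 (Design; Procedures), and one baseline and one post-trial measure of PERMA overall. The documents give no alpha, power, effect size, SD, correlation or dropout rate, so there is no figure of the plan's own to reproduce.

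**Assumptions.** Two-sided 0.05; effect d = 0.4 SD in both app arms unless stated; pre-post correlation r = 0.5 to 0.8; equal pre and post SDs unless stated; 50 or 40 completers per arm.

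**Step 1: variance per participant (post SD = 1, pre SD = k).**
- Change score: 1 + k² − 2rk, which is 2(1−r) when k = 1.
- Baseline-adjusted: 1 − r².
- Difference: (1 + k² − 2rk) − (1 − r²) = (k − r)², which is never negative and is zero only when k = r.
- Ratio, adjusted to change, when k = 1: (1−r²)/[2(1−r)] = (1+r)/2, giving 0.75, 0.80, 0.85 and 0.90 for r = 0.5, 0.6, 0.7 and 0.8.
- Ratio when k = 0.8: 0.89, 0.94, 0.98, 1.00. When k = 1.25: 0.57, 0.60, 0.63, 0.64.

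In sample-size terms (k = 1), change scores would need 150/0.75 = 200 participants at r = 0.5, or 150/0.85 ≈ 176 at r = 0.7, to match adjustment with 150.

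**Step 2: power for the same contrast, change score → adjusted.** Noncentral t with 3n−3 or 3n−4 df. The squared standard error is variance × 1.5/n for pooled app against waitlist and variance × 2/n for one arm against waitlist. Noncentral F is used for the 2-df test.

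| d = 0.4 | r = 0.5 | r = 0.6 | r = 0.7 | r = 0.8 |
|---|---|---|---|---|
| Pooled, 50 per arm | 63.1 → 75.5 | 72.7 → 81.8 | 84.2 → 89.5 | 95.2 → 96.9 |
| One arm vs waitlist at 0.025, 50 per arm | 39.8 → 51.9 | 49.0 → 59.4 | 62.5 → 70.4 | 81.4 → 85.6 |
| 2-df test, 50 per arm | 52.3 → 65.3 | 62.3 → 72.7 | 75.6 → 82.5 | 90.9 → 93.7 |
| Pooled, 40 per arm | 53.5 → 65.7 | 62.9 → 72.6 | 75.3 → 81.8 | 90.0 → 92.7 |

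With 50 per arm, the gain runs from about 2 to 13 points within a row. Over d = 0.3 to 0.6 and r = 0.3 to 0.8, the pooled gain runs from 0 to 18 points. A simulation of 10,000 trials per setting agreed (pooled, r = 0.6: 72.6 → 81.2; null rejection 5.1% and 5.3%). The second degree of freedom, for first responder/veteran, does not change these figures at the precision shown.

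**Step 3: what the mixed model does.** Variance of the pooled contrast at r = 0.6, 50 per arm:
- Complete data, free baseline means: 0.80 × 1.5/50 = 0.0240, the same as the change score.
- Complete data, common baseline mean: 0.64 × 1.5/50 = 0.0192, the same as ANCOVA.
- With 10 of 50 per arm missing post: common baseline mean 0.0240 (equal to complete-case ANCOVA), free baseline means 0.0288, complete-case change score 0.0300.

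**Step 4: does naming the contrast raise power in general?** Suppose only one app arm works (0.5 SD, r = 0.6, 50 per arm). The pooled contrast then sees an effect of 0.25 SD.

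| Test | Change score | Adjusted |
|---|---|---|
| Pooled app vs waitlist | 36% | 43% |
| That arm vs waitlist at 0.025 | 70% | 80% |
| 2-df test | 82% | 90% |

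Adjustment helps in every row. The choice of row can help or hurt: the unadjusted 2-df test (82%) exceeds both adjusted contrasts, although it answers a broader question. Even with equal effects, the adjusted per-arm power in Step 2 (52/59/70/86%) is equal to or below the unadjusted 2-df power (52/62/76/91%).

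**The case against.** The strongest reply is that the plan has not chosen the less precise model. It leaves the mixed model open, and a mixed model with a common baseline mean treats baseline as a repeated outcome and still matches ANCOVA. The mixed model is also the likelier branch: first responder/veteran is one of the plan's own clustering examples, and recruitment is capped at 75 in each of the two groups. This stands. A reader might infer from the pre-post wording that the plan commits to a change-score analysis. The documents do not support that, and the delta wording belongs to the exploratory correlations. What remains is that the plan never states a common baseline mean, and the alternative it names, repeated-measures ANOVA, does not provide one.

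A reader might also infer that stating the app-versus-waitlist contrast would itself raise power. Step 4 shows that it need not.

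A third tempting inference is that the primary outcome is in doubt. It is not: Primary outcome variable(s) names it plainly, and the Analysis Plan lists it first. The word secondary in the Analysis Plan is a labelling slip.

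Finally, this is a pilot feasibility trial with no power claim, both forms of analysis are valid, and every magnitude here rests on assumed d and r. That limits the stakes. It does not remove the stated aim of testing effectiveness.

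**Conclusion.** The point holds as a gap in specification with a modest, assumption-dependent cost. Repeated-measures ANOVA, and a mixed model with free baseline means on complete data, are valid but never more precise in large samples than baseline adjustment, whichever contrast is used. The direction follows from algebra; the size does not. At d = 0.4, r = 0.5 to 0.8, equal SDs and 50 per arm it is about 2 to 13 points of power. It is close to zero when d and r are both high, or when pre SD/post SD is about r. If the intended model is a mixed model with a common baseline mean, nothing is lost and only the wording needs changing.

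Relabelling the outcome and naming the test in advance are clarifications. The documents do not support treating either as a power gain, or treating the planned analysis as invalid.

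**What to change.** In the Analysis Plan:

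1. Analyse post-trial PERMA overall with baseline PERMA overall as a covariate (ANCOVA), or with a mixed model that has a common baseline mean across arms. Include first responder/veteran as a fixed factor, and keep a workplace random effect if participants share workplaces.
2. Use the same model for the other 12 scales, labelled as in the outcome sections: six under the primary domain (Positive emotion, PHQ-8, GAD-7, WHO-5, PWS, DERS-SF) and six as secondary (Engagement, Relationships, Meaning, Accomplishment, UWES, MBI).
3. For clarity, label PERMA overall as primary and name in advance the test that carries the app-versus-waitlist prediction: pooled arms, each arm with a multiplicity rule, or the 2-df test. The trade-off in Step 4 should inform that choice.

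The cost is two degrees of freedom (baseline and first responder/veteran) and no new data.

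Two matters lie outside this change. Adjustment does not deal with missing post-trial surveys, which need their own statement. Whether baseline is completed before the arm is disclosed is a separate procedural point: randomisation follows consent, and the survey may be finished at the intake meeting.

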### **Design**

The study is a three-armed randomized waitlist pilot feasibility trial with up to 150 participants (50 in GUIDE with incentives group [immediate access to GUIDE with incentives], 50 in GUIDE without incentives group [immediate access to GUIDE without incentives], 50 in waitlist group [waitlisted with delayed access to GUIDE without incentives]).

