### Accrual

This proposal involves the recruitment of 150 participants, including about 75 first responders/ corrections officers and 75 soldiers/veterans. Participation will be capped for each group using REDCap. To recruit these participants, the research team will rely on the GUIDE teams agency connections, existing partnerships, customers, and advisers. We do not anticipate difficulty meeting the recruitment and retention goals for this project because we have the GUIDE apps recruitment support, as well as the participant compensation at pre- and post-trial.

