## Consent

### 1. Consent Process

#### Overview

Once participants are recruited and communication is established, interested invitees will be prompted to complete a brief screener on REDCap to determine eligibility based on inclusion criteria. After eligibility is established, they will be directed to review the Informed Consent Form and HIPAA Authorization Form via REDCap. These consent forms include a description of the study and expected roles and responsibilities of the participant, risks and benefits to participants, and confidentiality procedures (see attached). The consent forms also clearly state that participation in the study is completely voluntary, and participants can drop out of the study without penalty at any time. All consent forms follow the guidelines outlined by the University of Pennsylvania, and ethical guidelines set forth by the state and federal governments. Documentation of subject consent will be stored in a locked file in the PI or designees office at each study site or in one of the HIPAA-compliant servers described above.

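### The rule choosing between a mixed model and repeated-measures ANOVA looks only at clustering, yet it also decides whether participants without a post-trial survey are analysed

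*Combined protocol and SAP*

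**What the plan says.** The Analysis Plan gives one rule for the pre-post scales: they "will be analyzed either using linear mixed models or repeated-measures ANOVA, depending on whether there are clustering variables". Its examples are "clustering variables (e.g., workplace, first responder/veteran". The sentence speaks of secondary outcomes, but the list that follows it opens with the primary one: "Key measures used for this analysis will be the: PERMA-Profiler overall wellbeing score and subscales". The section on primary outcome variables confirms this: "The primary outcome variable will be the overall wellbeing score of the PERMA-Profiler". The predictions are stated for app users "when compared to the waitlist group".

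The Design section describes a "three-armed randomized waitlist pilot feasibility trial with up to 150 participants (50 in GUIDE with incentives group", with 50 in each of the other two arms. Each scale is collected at baseline and once after the four-week period. Randomisation follows consent, and the baseline survey comes after consent and can be left until the intake meeting.

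On dropout, the consent Overview says "participants can drop out of the study without penalty at any time", and the Accrual section says "We do not anticipate difficulty meeting the recruitment and retention goals for this project". No expected rate is given. The document has no definition of the analysis population, no intention-to-treat statement, no method for missing outcomes and no sensitivity analysis.

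**The concern.** Whether the data are clustered and whether some outcomes are missing are separate questions, and the plan lets the first answer the second. The plan does not say in words that ANOVA is used when there is no clustering, but that is the natural reading. With two time points, the group-by-time test in a standard repeated-measures ANOVA is a comparison of mean change scores among people who have both surveys. Anyone randomised who returns only the baseline drops out of the comparison.

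Completers need not resemble the randomised groups. If the people who leave one arm have unusually low (or high) baseline wellbeing, those who remain start higher (or lower) and tend to move back toward the mean. Their change scores carry that movement, and the contrast between arms absorbs it. The primary PERMA score is on the list of scales affected.

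**Working it through.** The documents give no power calculation, SD, correlation, effect size or dropout rate, so there is no stated figure to reproduce beyond 3 x 50 = 150. Every input below except the 50 per arm is an assumption.

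**Inputs.** One app arm against waitlist; two time points; SD 1 at each; true effect 0.30 SD; pre-post correlation r = 0.6, with 0.5 and 0.7 as checks. App-arm loss is 20% or 30%, with log-odds of dropout changing by 0.5 or 1 per SD of baseline, in either direction. Waitlist loss is 10%, at random unless stated.

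**Formula for the ANOVA branch.** Let m be the mean baseline of an arm's completers, in SD from the mean of all randomised. Their expected post score is r x m plus any effect, so their mean change carries an extra (r - 1) x m. Hence

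bias = -(1 - r) x (m_app - m_waitlist).

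Random dropout gives m = 0. Integrating over a normal baseline gives the m values below for loss concentrated at low baseline; loss at high baseline reverses the signs.

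| App-arm loss | Log-odds slope per SD | m_app | Bias at r = 0.6 |
|---|---|---|---|
| 20% | -0.5 | 0.096 | -0.4 x 0.096 = -0.038 |
| 30% | -0.5 | 0.143 | -0.4 x 0.143 = -0.057 |
| 20% | -1 | 0.173 | -0.4 x 0.173 = -0.069 |
| 30% | -1 | 0.253 | -0.4 x 0.253 = -0.101 |

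Simulation (4,000 trials per setting) gave -0.035, -0.056, -0.068 and -0.100 for the same rows, and +0.040, +0.059, +0.069 and +0.099 with the sign reversed. The maximum-likelihood estimate using all baselines had bias between -0.002 and +0.003, with about the same standard error (0.19-0.20).

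**Other correlations.** With 30% loss and slope -1, the bias is -0.5 x 0.253 = -0.126 at r = 0.5 and -0.3 x 0.253 = -0.076 at r = 0.7. A large-sample simulation gave -0.126 and -0.076, and about 0.00 for the mixed model.

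**Small-sample check.** With 50 per arm, r = 0.5, about 30% app-arm loss and 300 runs, the mean ANOVA estimate was 0.161 (Monte Carlo standard error 0.013) and the mean mixed-model estimate 0.286, against a true 0.30.

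**When the bias shrinks or vanishes.** Suppose low-baseline dropout with slope -1 operates in both arms, at 20% versus 10%. The waitlist completers then shift by 0.091, and the bias is -0.4 x (0.173 - 0.091) = -0.033. Unequal loss completely at random (30% versus 10%) gives none, and neither does equal loss with the same mechanism (20% in each arm).

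**When the mixed model is not protective.** Let app-arm dropout depend on the unseen post score instead. If completers' post mean is shifted by s, their baseline mean is shifted by r x s. The change-score bias is s x (1 - r). The mixed model recovers only the part predictable from baseline, leaving about s x (1 - r squared), which is larger by a factor of about 1 + r. At r = 0.6 with the losses and slopes above, the ANOVA bias is 0.04-0.10 SD and the mixed-model bias 0.06-0.17 SD. At r = 0.5, 30% loss and slope -1, the simulated figures were +0.127 and +0.193.

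**The case against.** The strongest reply is that the ANOVA branch may never be used. The plan names first responder versus veteran as a clustering variable, and that split is built into recruitment, with about 75 in each group and a REDCap cap. Recruiting through agencies also makes workplace clustering plausible. This stands: a reader might infer that the primary result will come from ANOVA on completers, and the document does not say so. It leaves the branch open, and any protection from the mixed model would be a by-product of the clustering rule.

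A reader might also infer that dropout will be unequal. The document does not show that. Survey pay is the same in all arms ($50 twice). The extra money, up to $100, goes to one of the app arms and would tend to keep its members in. The waitlist is offered the app at the post-trial meeting, and unfinished surveys can be completed there in every arm. Retention is listed as a feasibility measure, so some reporting of it is planned, though not explicitly by arm. Motives to stay do differ between arms, but in which direction is unknown, and unequal rates alone do not cause bias.

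The sizes are also modest. The largest figure in the r = 0.6 range, 0.10 SD, is about half the standard error of 0.19-0.20. It is a third of the assumed effect (0.10 / 0.30), but that ratio divides one assumption by another. The trial is a pilot. Even so, the Abstract sets out to test effectiveness and the Analysis Plan makes directional predictions against waitlist, so these contrasts will be read as results.

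**Conclusion.** The point holds in conditional form. The rule ties the choice of model to clustering alone, and that choice also determines whether baseline-only participants are analysed. If ANOVA is used and dropout depends on baseline differently by arm, the app-versus-waitlist contrast is biased by about 0.04-0.10 SD at r = 0.6 with 20-30% app-arm and 10% random waitlist loss. The bias is about 0.03 SD with the same mechanism in both arms at 20% versus 10%. A likelihood mixed model has bias near zero in those cases.

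Two stronger conclusions are not supported. The documents do not show that the planned results are biased, because they give no dropout rate and do not settle which branch applies. Nor is the mixed model a full cure: it relies on dropout being explained by observed data, and when dropout follows the post score it can do worse than ANOVA. The case for preferring it is that it uses all available data under a weaker assumption that can be stated and then tested by a sensitivity analysis.

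**What to change.** In the Analysis Plan, replace the either/or with text such as:

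> Every pre-post outcome is analysed by a linear mixed model (ML/REML, unstructured pre-post covariance) whether or not clustering is present. The model includes all randomised participants with at least one survey, in the arm assigned, under a missing-at-random assumption. Random or fixed effects for clustering are added where present. Repeated-measures ANOVA is not used. The number randomised, the number with neither survey and post-trial completion are reported by arm. A sensitivity analysis shifts missing post-trial outcomes over a stated range (for example 0.2 and 0.5 SD).

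The condition of at least one survey is needed because randomisation follows consent and can precede the baseline survey; someone with neither survey cannot enter any likelihood model and should be counted openly. The shift values are examples, and the team should choose and justify its own range before seeing outcome data.

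The cost is a short edit and slightly more analysis work, with no new data. The price in interpretation is reliance on a stated missing-at-random assumption, which is why the sensitivity analysis belongs in the same edit.
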